The largest clinical experience using MW ablation to treat HCC comes from China, in part due to early adoption of MW ablation systems available only in Asia. That multicenter study of 1007 patients with primary liver cancer showed a technical success of 97.1% (1276/1363) and a local tumor progression rate of 5.9% (78/1363) with a mean follow-up time of 17.3 months (range, 3-68.9 months). The 1-, 3- and 5-year overall survival rates were 91.2%, 72.5% and 59.8%, respectively.⁵

A retrospective study of MW ablation as a first-line treatment for HCC evaluated the long-term outcomes and prognostic factors of 221 consecutive patients receiving MW ablation in Renji Hospital (Shanghai) between October 11, 2010 and December 31, 2013 were enrolled. Technique effectiveness was evaluated 1-month post-ablation. Initial complete ablation was found in 201 (90.95%) patients, secondary technique effectiveness in 8 (3.62%) patients, and the remaining 12 (5.43%) patients suffered from incomplete ablation after 2 sessions of MW ablation. No patients died within 30 days post ablation. Major complications occurred in 8 (3.8%) patients. It was concluded that MW ablation provides high technique effectiveness rate and is well tolerated in patients with HCC as a first-line treatment.

Confidential Page 21 of 61

Literature Review

Pre-clinical and clinical data has shown that MW ablation is safe and effective in liver tumors with low complication rates, high rates of technical success, lower rates of local tumor progression and promising disease-free and overall survival rates than have historically been reported for radiofrequency (RF).⁷

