The number and percentage of tumors achieving Technical Success will be summarized and a 95% confidence interval will be estimated. Technical Success will be evaluated based on the margin achieved after the first ablation and prior to any repeat ablations within the first 7 days.

A similar summary will be provided for Technical Efficacy. This endpoint will be based on the scan obtained at Visit 3 and will count as successes patients with A0 or A1 margins in that scan and who did not have an A2 margin since the Visit 2B scan. Additionally, if a patient received a repeat ablation for correcting a margin (to go from A1 to A0) within the first 30 days, this will also count as a success. Patients with repeat ablations to correct an A2 margin from Visit 2B to Visit 3 will not count as success for Technical Efficacy. The number and percentage of tumors with A0 and A1 margins will be presented as a subcategorization within each presentation of Technical Success and Technical Efficacy, as well as a summarization for the number and reasons for repeat ablations through Visit 3.

Local tumor progression rates at 1, 3, 6, 9, 12, 18, 24, 30, and 36 months will be estimated using the Kaplan-Meier method and 95% confidence intervals will be provided. Any repeat ablation required after Visit 3 (Month 1) will be identified as an instance of local tumor progression. A similar summary will be provided for the 36-month overall and progression-free survival rates.

Confidential Page 41 of 61

The number and percentage of patients experiencing AEs will be summarized at the preferred term level using the Society of Interventional Radiology (SIR) clinical practice guidelines for event categorization. A similar summary will also be provided for device-related AEs, procedure-related AEs, all SAEs, device-related SAEs, and procedure-related SAEs. Adverse event rates will also be estimated using cumulative patient years of exposure as the denominator as well as total number of patient ablations.

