A subject archieving technical efficacy is defined as a patient with all tumors reaching A0 or A1 at Visit 3. The number and percentage of subjects archieving Technical Efficacy will be summaried as well. Percentage will be calculated relative to the total number of subjects in relavent analysis population (FAS or PPS). A 95% confidence interval will be estimated using wald method. But the subjects who have any A2 margin since the visit 2B scan would not be counted as technical efficacy regardless if the tumor was corrected with repeat ablation.

Local tumor progression (LTP) (the 2nd interim, final)

LTP is evaluated after the ablation of the target tumor(s). LTP describes the appearance of tumor foci at the edge of the ablation zone, after at least one contrast-enhanced follow-up

MRI scan has documented adequate ablation, and an absence of viable tissue in the target tumor and surrounding ablation margin, by using imaging criteria.

Tumor-level analysis method is same as that of Technical Success endpoint. The number and percentage of tumors with LTP will be summarized and a 95% confidence interval will be estimated using Wald method.

A subject with LTP is defined as a patient with any target tumor LTP. The number and percentage of subjects with LTP. Percentage will be calculated relative to the total number of subjects in relevant analysis population (FAS or PPS).

Subgroup analysis is defined in SAP section 8.11. Two subgroup columns (subjects/tumors with only initial ablation and subjects/tumors with repeat ablation) and 1 total column will be used as analysis columns in LTP tables.

Tumor type (primary HCC and recurrent HCC and other) will be another subgroup variable for LTP (analyzed for patient level and tumor level).

LTP start date is the date of initial ablation of a subject. The event date of LTP is collected in "Ablation Zone Assessment" CRF page as following table:

		Event/Censoring	
	Situation	Date	Outcome
No post-base	eline or no baseline Ablation Zone A	ssessment	
	No post-baseline local tumor	Date of initial	
A1	evaluation	ablation	Censored
	No baseline local tumor	Date of initial	
A2	evaluation	ablation	Censored
With baselin	e and post-baseline tumor assessm	ents	
	Local Tumor Progression and zero or one missed tumor assessment prior to confirmed		
B1	LTP	Date of first LTP date	Event

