	Local Tumor Progression and over one missed tumor assessment prior to confirmed	Date of the latest evaluable local tumor assessment prior to the missed	
B2	LTP	assessment	Event
		Date of last local	
		tumor assessment	
	No progression, either alive or	with no documented	
С	death	LTP	Censored

Table 3: Censoring Rules for LTP

		Date of last tumor assessment with no documented	
D	Dead	progression	Censored
		Date of last tumor	
		assessment with no	
		documented	
E	Withdrawal by Subject	progression	Censored

Local tumor progression rates at 3, 6, 9, 12, 18, 24, 30, and 36 months will be estimated using the Kaplan-Meier (K-M) method and 95% confidence intervals (Greenwood's formula) will be provided.

The K-M curve of time to LTP will be provided.

Secondary efficacy rate (the 2nd interim, final)

Secondary efficacy rate is defined as the percentage of subjects whose tumors have undergone successful repeat ablation following identification of local tumor progression at any time during study follow up.

It could be found in CRF page, Ablation Zone Assessment, "Re-ablate with Neuwave". For subgroup that has LTP and used Certus to re-ablate, the number and percentage of subjects achieving secondary efficacy, will be summarized and a 95% confidence interval will be estimated using wald method.

Progression-free survival (PFS) (the 2nd interim, final)

PFS is defined as length of time from initial ablation until disease progression.

Table	e 4. Censoring Rules for PFS		
	Situation	Event Date	Outcome
No po	st-baseline or no baseline Ablation Zo	ne Assessment	
	No post-baseline tumor evaluation		
A1	and alive	Date Ablation performed	Censored
	No post-baseline tumor evaluation		
	but died on or before the second		
A2	scheduled tumor assessment	Date Ablation performed	Censored
With baseline and post-baseline tumor assessments			

Table 4: Censoring Rules for PFS

В	Any Tumor Progression and zero or one missed tumor assessment prior to progression	Date of first progression	Event
		Date of last progression	
	PD happens after >=2 consecutively	assessment before	
С	missing tumor assessment	missing assessments	Censored
		Date of last progression	
		assessment with no	
D	No progression	documented progression	Censored

Progression-Free Survival rate will be estimated using the Kaplan-Meier method and 95% confidence intervals (Greenwood's formula) will be provided for 6, 12, 18, 24, 30, 36 months.

The K-M curve of time to progression will be provided.

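### The planned Kaplan-Meier LTP rates censor deaths, so they estimate net LTP risk as if no one died, which is at or above a treated patient's probability of LTP; add a cumulative incidence with death as a competing event

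*SAP*

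**What the plan says.** SAP 8.4.1 sets the LTP estimator: "Local tumor progression rates at 3, 6, 9, 12, 18, 24, 30, and 36 months will be estimated using the Kaplan-Meier (K-M) method", with Greenwood 95% limits. Protocol 8.1 names the same method and adds month 1: "Local tumor progression rates at 1, 3, 6, 9, 12, 18, 24, 30, and 36 months will be estimated".

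Table 3 of the SAP gives the censoring rules. Row C, which begins "No progression, either alive or" and ends with death, censors at the last local tumor assessment free of LTP. Row D covers patients who are dead, and row E covers withdrawals. Both D and E censor at the same point: "Date of last tumor assessment with no documented" progression. A death without LTP is therefore treated exactly like a withdrawal, and it fits two rows at once.

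The SAP also plans a crude figure: "The number and percentage of tumors with LTP will be summarized and a 95% confidence interval will be estimated using Wald method". A patient-level percentage is planned as well, over all patients in the Full Analysis Set or Per Protocol Set.

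Death is an event for overall survival and in the sensitivity analysis of progression-free survival. LTP has no counterpart, and neither document mentions competing risks or cumulative incidence.

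**The concern.** A patient who has died can no longer develop LTP. Censoring that patient lets those still under observation stand in for the patient's LTP experience after death. The result is a net risk, meaning LTP risk if death were removed. It can be read that way only if death and LTP are independent, and the SAP states neither the target nor the assumption. It cannot fall below the probability that a treated patient has LTP by month 36, and it exceeds that probability when deaths come before later LTP.

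The difference matters because the trial has no hypothesis and no acceptance threshold. Protocol 8.4 judges performance by looking at all the data in the context of other HCC therapies, so the estimates themselves carry the conclusion. The LTP benchmark in the protocol's background is a crude proportion, and one minus Kaplan-Meier is a different quantity. Deaths should not be rare on the protocol's own source: "The 1-, 3- and 5-year overall survival rates were 91.2%, 72.5% and 59.8%, respectively" in the cited multicenter series of 1007 patients, so 27.5% had died by 3 years.

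**Working it through.** **No LTP figure to reproduce.** Neither document states or assumes a 36-month LTP rate for this trial. The one planning figure, the sample size, reproduces: 100/(1 − 0.20) = 125, plus 12 run-in patients = 137.

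**Inputs (Protocol 4.1.1, cited Chinese multicenter series; used here as assumptions).**
- Survival of 91.2% at 1 year and 72.5% at 3 years.
- LTP: "local tumor progression rate of 5.9% (78/1363) with a mean follow-up time of 17.3 months". The fraction 78/1363 is in fact 5.7%; the effect is shown below.

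**Hazards per month.**
- Death, months 0–12: h1 = −ln(0.912)/12 = 0.00768.
- Death, months 12–36: h2 = −ln(0.725/0.912)/24 = 0.00956.
- LTP, constant: λ = −ln(1 − 0.059)/17.3 = 0.00352.

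**What Kaplan-Meier targets at 36 months.** 1 − exp(−36λ) = 1 − exp(−0.1265) = 11.9%.

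**Cumulative incidence with death competing.**
- Months 0–12: λ/(λ+h1) × [1 − exp(−12(λ+h1))] = 0.3141 × 0.1257 = 0.0395.
- Months 12–36: exp(−12(λ+h1)) × λ/(λ+h2) × [1 − exp(−24(λ+h2))] = 0.8743 × 0.2688 × 0.2694 = 0.0633.
- Sum: 10.3%.

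The gap is 11.9 − 10.3 = 1.6 points, and 0.1189/0.1028 = 1.16, about 16% relative. At 12 months the values are 4.13% and 3.95%, a gap of 0.2 points. With 78/1363 in place of 5.9%, the 36-month pair is 11.5% and 10.0%, and the relative excess is unchanged.

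**Range.** The death hazard was multiplied by 0.5, 1 and 1.5. Entries are one minus Kaplan-Meier minus cumulative incidence at 36 months. The net LTP values other than 11.9% are assumed.

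| Net LTP at 36 months | 15% dead | 27.5% dead | 38% dead |
|---|---|---|---|
| 5% | 0.4 points | 0.7 | 1.0 |
| 11.9% (cited figures) | 0.8 | 1.6 | 2.3 |
| 20% | 1.4 | 2.7 | 3.8 |
| 30% | 2.1 | 3.9 | 5.6 |
| 40% | 2.7 | 5.1 | 7.2 |

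The relative excess is about 7–8% at 15% mortality, 15–16% at 27.5%, and 22–24% at 38%.

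**Simulation on the SAP visit schedule.** There were 125 patients with one tumor each, censoring at the last scan as in Table 3, and 800 runs. Hazards are those from the cited figures.

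| Dropout | One minus Kaplan-Meier | Aalen-Johansen | Crude patient percentage | Kaplan-Meier 95% half-width |
|---|---|---|---|---|
| 0% | 11.8% | 10.0% | 10.0% | 6.1 points |
| 20% | 11.9% | 10.0% | about 9.0% | 6.6 points |

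With no dropout, the crude percentage and the cumulative incidence coincide. With 20% dropout, the crude percentage falls about one point short. Aalen-Johansen sits slightly below the closed-form 10.3% because LTP that arises after the last scan before death is never seen.

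**The case against.** The strongest reply is that Kaplan-Meier is not wrong here. LTP describes control of the treated lesion, and net local failure is a legitimate target for a device. If death is independent of LTP, one minus Kaplan-Meier estimates it without bias. The protocol specifies this method, and no passage says that the probability of observed LTP is the intended quantity. This stands: the documents leave the target unstated, and one cannot call Kaplan-Meier an error without first choosing a target.

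A figure close to the alternative is also planned. The patient-level crude percentage keeps deaths in its denominator, every patient is scheduled for 36 months, and the final analysis waits for all of them to finish. Death does not bias that percentage. This stands too, but dropout does bias it, because patients lost early count as free of LTP. Both documents allow for up to 20% dropout.

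The gap is small, lies inside the confidence interval, makes the device look worse rather than better, and feeds no decision rule. All of that is correct. It limits the weight of the point but does not remove it: unlike sampling error, this difference does not shrink with more patients.

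A reader might infer that the trial's 36-month LTP rates are overstated. The documents do not support that. They contain no such rate, and overstatement follows only if the rate is read as the probability that a treated patient has LTP by that month.

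**Conclusion.** The concern holds as a gap in the planned estimator and in what it is said to estimate. Once deaths and dropout occur, no planned figure gives the probability of LTP by each month: one minus Kaplan-Meier is at or above it, and the crude patient percentage is below it because of dropout. On the cited figures the three are 11.9%, about 10% and about 9.0% at 36 months.

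The size is modest: 1.6 points against a half-width of about 6.6, and negligible at 12 months. At the cited mortality the gap reaches about 4 points only when net LTP is near 30%. The calculation assumes a constant LTP hazard, independence of LTP and death, and one tumor per patient. Survival and LTP are borrowed from another cohort. Protocol 7.1.5 also admits recurrent HCC, Child-Pugh B and ECOG 2, so mortality may differ, which is why a range is shown.

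The change is worth making because it is cheap and the results will be read against other therapies. It does not threaten the trial's conclusions.

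**What to change.** 1. In SAP 8.4.1, state what the LTP rate is meant to estimate.
2. At each listed month, report the Aalen-Johansen cumulative incidence of LTP with 95% confidence limits and death before LTP as a competing event. Place it alongside the protocol-specified Kaplan-Meier estimate, and label the latter as net risk with deaths censored.
3. In Table 3, split row C. Patients alive without LTP stay censored at the last local tumor assessment. Merge the death part with row D and code it as a competing event at the date of death. This also removes an overlap: rows C and D can give one death two different dates if non-local progression came first.

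The cost is SAP wording, one extra event code and one extra curve to explain. The SAP already refers to a CRF page for deaths. One limitation should be recorded: late scans are six months apart, so LTP arising between the last scan and death goes uncounted. The cumulative incidence is therefore of detected LTP and may be slightly low.

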7.1.2. Trial Endpoints

Efficacy Endpoints

The efficacy endpoints are defined, as follows:

- Technical Success, defined as a combination of A0 ablations (complete tumor ablation with a surrounding 5 mm margin) and A1 ablations (complete tumor ablation with inadequate margins) based on contrast-enhanced MRI performed up to 7 days following the original ablation procedure.
- Technical Efficacy, defined as a combination of A0 ablations (complete tumor ablation with a surrounding 5 mm margin) and A1 ablations (complete tumor ablation with inadequate margins), based on contrast-enhanced MRI scans at 1 month (+/- 7 days) after the original ablation procedure.
- Local tumor progression (LTP), evaluated at every visit after the ablation of the target tumor(s). LTP describes the appearance of tumor foci at the edge of the ablation zone, after at least one contrast-enhanced follow-up MRI scan has documented adequate ablation and an absence of viable tissue in the target tumor and surrounding ablation margin by using imaging criteria.
- Secondary efficacy rate, defined as the percentage of tumors that have undergone successful repeat ablation following identification of local tumor progression at any time during study follow up.
- Progression-free survival, defined as length of time from the original ablation procedure until any type of disease progression (i.e. local or distant).
- Overall survival measured from the time of the original ablation procedure to the time of death or last follow-up if death has not occurred.

Confidential Page 26 of 61

Safety Endpoint

The safety endpoint is the rate of AEs and SAEs reported at each analysis and cumulatively throughout the entire study period.

Patient Reported Outcomes:

- Pain, as measured by Numeric Pain Rating Scale, before the ablation procedure (measured at Screening Visit), post ablation (within 7 days after ablation]), and at the 1-month follow-up visit.
- Quality of Life, as measured by EORTC QLQ-C30 and liver-specific EORTC QLQ-HCC18, before the ablation procedure (measured at Screening Visit), post ablation (within 7 days after ablation), and at each follow-up visit.

Health Economics:

 Health economics associated with the ablation procedure, including complete procedure time, ablation time, number of ablations, number and types of probes, change in probe position, number of computed tomography (CT) and ultrasound scans performed for probe and margin assessment, and length of hospital stay.

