The expected overall duration is approximately 65 months, including the time that each site's Ethics Committee takes to approve the trial protocol, institution contract sign-off, Human Genetic Material Office approval, duration of patient enrollment, duration of follow-up, time for data management, statistical analysis, and time to write, review and approve the clinical study report.

6) Expected duration of participation of each patient

The duration of each patient's participation in the study will be around 37 months (about 1 month for Screening and 36 months for follow-up). The follow-up schedule will be based on the original ablation procedure date. A re-ablation for any reason will not change or extend the follow-up visit schedule.

7) Number of patients required for clinical trial

This study will include 137 patients, of which 3 patients per site (n=12) will be part of the runin phase. This is a single-arm study, and hence there will be no randomization of patients. See Section 8.2 "Calculation of Sample Size" for the basis for selecting this sample size.

Confidential Page 30 of 61

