06 AUGUST 2020, VERSION: 4.0

- Length of hospital stay.
- Complete tumor ablation evaluation.
- Any update to relevant concomitant medications.
- Relevant concomitant procedures.
- All AEs and SAEs.

Post Ablation Follow-up Visits 3 to 11 (End of Study)

The following data will be collected post ablation at the post ablation follow-up visits, from Visit 3 through the end of the study (Visit 11), as follows:

- Pain score, using the NPRS (Visit 3 only).
- Quality of Life questionnaires: NPRS pain score, EORTC QLQ-C30 and liver-specific EORTC QLQ-HCC18.
- MRI of the liver.
- Laboratory tests.
 - Coagulation tests (PT, APTT, and INR).
 - Liver function tests (AST, ALT, GGT, albumin, indirect, direct and total bilirubin, and total protein).
 - o Renal function test (Urea, creatinine, and electrolytes [sodium, potassium, and chloride]).
 - Complete blood count (differential cell count and platelet count).
 - Alpha-fetoprotein (AFP) test.
- ECOG performance status.
- Complete tumor ablation evaluation (Visit 3 only)
- Local tumor progression (LTP) to be evaluated by a study physician based on MRI imaging. All MRI scans are to be submitted to the Sponsor.
- Progression-free survival to be evaluated by a study physician based on MRI imaging or may be reported by a patient's primary treating oncologist, if different than the study physician. If there is a progression, the study physician should specify if the progression is of the original target tumor, a new HCC tumor in the liver, or a distant metastasis.
- Any update to relevant concomitant medications.
- Relevant concomitant procedures.
- All AEs (if within 30 days post an ablation procedure).
- All SAEs through end of study.

Confidential Page 39 of 61 06 AUGUST 2020, VERSION: 4.0

Note: Repeat ablations may be performed on target tumor(s) only.

Unscheduled Visits

The following data will be collected at all unscheduled visits:

- Reason for the unscheduled visit.
- Relevant concomitant medications.
- Relevant concomitant procedures.
- AEs (if within 30 days post an ablation procedure) and all SAEs.

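### Secondary efficacy moves from tumors in the protocol to re-ablated subjects in the SAP, and neither document says what makes a repeat ablation successful

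*SAP*

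**What the plan says.** Protocol 7.1.2 (repeated in the synopsis and in 7.1.6) sets the endpoint at tumor level: "Secondary efficacy rate, defined as the percentage of tumors that have undergone successful repeat ablation following identification of local tumor progression". It states no denominator and does not say what counts as successful.

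SAP 8.4.1 changes the unit: "Secondary efficacy rate is defined as the percentage of subjects whose tumors have undergone successful repeat ablation following identification of local tumor progression". For the data it says "It could be found in CRF page, Ablation Zone Assessment" and names the item *Re-ablate with Neuwave*. The one summary it specifies is: "For subgroup that has LTP and used Certus to re-ablate, the number and percentage of subjects achieving secondary efficacy", with a Wald 95% interval, at the second interim and final analyses.

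The grading that could define success is listed in Protocol 7.2.4 as "Complete tumor ablation evaluation". It appears under Visit 2B and, for Visits 3 to 11, is marked for Visit 3 only; Table 1 of the protocol agrees. A later re-ablation does not bring its own visits: "A re-ablation for any reason will not change or extend the follow-up visit schedule" (Protocol 7.1.5).

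**The concern.** The rate is meant to show how well a local recurrence can be controlled by repeating the procedure. Three things stand in the way.

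- **Unit.** The SAP analyses Technical Success, Technical Efficacy and LTP by tumor and by subject, but this endpoint by subject only. A subject can have up to three target tumors, and nothing says how to count one with two LTP tumors of which one was successfully re-treated.
- **Success.** Technical Success and Technical Efficacy each have a grade (A0 or A1) and a named visit. Secondary efficacy has no grade, scan or window, so two programmers could produce different results from the same data.
- **Denominator.** Repeat ablation is at the treating physician's discretion (Protocol 7.2.2). Subjects with LTP who are not re-ablated leave the calculation, so the rate describes re-treatment rather than control of recurrence among everyone who had one.

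Protocol 8.4 sets no acceptance criterion and judges performance from all the data together. A rate with an unclear meaning would feed into that judgement.

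**Working it through.** **Scale.** The plan states no figure for secondary efficacy. Its only design figure reproduces and is not in dispute: 100 / (1 − 0.20) = 125, plus 3 × 4 = 12 run-in patients, gives 137. The 125 main-phase subjects set the scale here.

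**Timing of grading against timing of re-ablation.**
1. LTP requires an earlier follow-up MRI that documented adequate ablation (Protocol 7.1.2), and Table 1 starts the LTP evaluation at Visit 3.
2. Any repeat ablation required after Visit 3 is counted as LTP (Protocol 8.1).
3. Re-ablations for LTP therefore fall mostly after Visit 3, the last visit with a scheduled A0/A1/A2 evaluation.
4. The SAP's LTP analysis does not fill the gap. Table 3 dates the event from the first LTP, and no rule covers a tumor's status after re-ablation.

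**Unit.** Take one subject with two LTP tumors, both re-ablated, one successfully. Per tumor the contribution is 1/2. Per subject it is 0/1 or 1/1, depending on a rule that the SAP does not give.

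**Denominator.** At a fixed unit let L be the cases with LTP, R those re-ablated with Certus, and S those successful, so S ≤ R ≤ L. Then

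S/R = (S/L) × (L/R), with L/R ≥ 1.

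The re-ablated-only rate is never below the all-LTP rate, and the two are equal when R = L. The documents give none of L, R or S, so the following are assumptions:

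- LTP in 5.9% to 20% of 125 gives about 7 to 25 subjects (125 × 0.059 = 7.4; 125 × 0.20 = 25). The 5.9% is the tumor-level rate printed in the protocol's background section and is used only for scale.
- If 50% to 100% of LTP cases are re-ablated, L/R runs from 2 down to 1.

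| L | R | S | S/R | S/L |
|---|---|---|---|---|
| 12 | 8 | 6 | 75.0% | 50.0% |
| 25 | 18 | 14 | 77.8% | 56.0% |
| 25 | 25 | 20 | 80.0% | 80.0% |

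**If the re-ablation item were also taken as success.** Then S = R and the rate is 100%. The Wald half-width is 1.96 × √(1 × 0 / R) = 0, so the interval is 100% to 100%. Exact 95% lower limits, 0.025^(1/R), would be 63.1% for 8/8 and 81.5% for 18/18.

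**The case against.** The strongest reply is that the protocol fixes no denominator. Its wording can be read as successes among re-ablated tumors, in which case the SAP is specifying the protocol rather than departing from it. The SAP names its subgroup openly, and a rate among re-treated cases is a fair description of the device on re-treatment; an all-LTP rate also mixes in the decision whether to re-treat. The SAP separately reports the number of subjects with LTP, so the all-LTP proportion per subject can be worked out. This stands. A reader might infer that the reported rate is inflated, but the documents do not show that: it is higher only relative to one choice of denominator, and not at all if every LTP case is re-ablated.

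A reader might also infer that success is not measured. That goes too far. MRI and LTP evaluation continue at every visit to Month 36, and the SAP places the A0/A1/A2 evaluation on the same CRF page as the re-ablation item. The Visit 2B data are due within 7 days of *an* ablation procedure, which could be read to cover repeat ablations. The outcome could probably be derived; what is missing is the rule and a scheduled grading.

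Finally, a reader might infer that the rate tends to 100% because it is read from *Re-ablate with Neuwave*. The CRF is not among the documents, the SAP keeps the word successful in its definition, and the item may serve only to identify the subgroup. The 100% result is one possible misreading, not what the SAP prescribes.

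The endpoint is descriptive, one of six for efficacy, and no decision rule depends on it. That limits the consequence. It does not answer the change of unit, the missing success rule or the absence of grading after Visit 3.

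**Conclusion.** The point holds in this form. The SAP reports a different unit from the protocol, gives no rule for subjects with several LTP tumors, and leaves success undefined. The only scheduled completeness grading comes before most of the re-ablations that the endpoint concerns. As written, the protocol's endpoint is not delivered.

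The direction of the denominator effect is certain at a fixed unit: equal or higher, never lower. Its size is unknown. Under the assumed 50% to 100% re-ablation share, the re-ablated-only rate is 1 to 2 times the all-LTP rate, and the tabulated percentages rest entirely on assumed counts. The re-ablated-only rate is a legitimate quantity; the fault is that it stands alone. This should be changed before the second interim analysis, where the endpoint is first reported.

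**What to change.** In SAP 8.4.1:

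1. Report secondary efficacy per tumor, as in the protocol, with the subject level as a second line. State the rule for several LTP tumors; requiring all of a subject's LTP tumors to succeed would match the SAP's subject-level rule for Technical Success.
2. Define success as A0 or A1 on the first MRI after the repeat ablation, and complete the existing A0/A1/A2 item at that already scheduled MRI.
3. State the allowed window from re-ablation to that MRI, and how a tumor with no later MRI is counted. Both are needed because visits are six months apart after Month 12 and a re-ablation near Month 36 may have no later scan.
4. Show the rate both among re-ablated LTP tumors and among all LTP tumors.
5. Say that *Re-ablate with Neuwave* identifies the re-ablated cases and is not the success indicator.

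The cost is SAP wording and one existing CRF item completed at more visits; no extra imaging is required. The all-LTP rate may look less favourable. A late scan may not separate an incomplete re-ablation from new progression, so the time from re-ablation to the graded MRI should be shown with the rate.

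Separately, with denominators this small an exact or Wilson interval would behave better than Wald, which gives 45% to 105% for 6/8.
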